4.2 Patient Disposition

The number and percentage of patients enrolled and treated in the study will be presented along with the number and percentage of patients in each analysis population. In addition, the number and percentage of patients who withdrew from study treatment and who discontinued the study for each reason will be tabulated.

Patient disposition data will be listed.

4.3 Protocol Deviations

The number and percentage of patients with any important clinical study report (CSR) reportable protocol deviation will be summarized overall and by type of deviation. The pre-defined important CSR reportable protocol deviations are listed below; in addition, any other protocol deviations deemed by ADCT medical to be important CSR reportable deviations will be included in the summary.

1. Patient entered the study even though they did not satisfy the entry criteria
2. Patient received a prohibited concomitant treatment during the study
3. Patient who met criteria for mandatory withdrawal of study drug during the study but did not have study drug withdrawn
4. Patient who received the wrong treatment or incorrect dose, specifically:
 - Actual dose of study drug was greater than 15% more or less than protocol defined planned dose level.
 - Patient started next cycle less than 18 days after Day 1 of the most recent treatment cycle.

Important protocol deviations will be listed.

4.4 Demographic and Baseline Characteristics

Demographic and baseline characteristics will be tabulated for the all-treated population. Variables include the following:

- Sex (female, male)
- Race (white, black or African American, Asian, American Indian or Alaska native, native Hawaiian or other Pacific Islander, other)
- Ethnicity (Hispanic or Latino, not Hispanic or Latino)
- Age (years)
- Age group (< 65, ≥ 65 - < 75, ≥ 75 years)
- Height (cm)
- Weight (kg)
- Body mass index (BMI) (kg/m²)
- Eastern Cooperative Oncology Group (ECOG) performance status

Demographic and baseline characteristics data will be listed.

4.5 Cancer History and Medications History

Cancer history will be presented for the all-treated population. Cancer history will include the following variables:

- Duration since diagnosis

- Diffuse large B-cell lymphoma subtype (NOS, Primary Mediastinal, and High-grade B-cell Lymphoma, with MYC and BCL2 and/or BCL6 rearrangements)
- DLBCL additional subtype (germinal center B-cell [GCB]/activated B-cell [ABC], double/triple hit, transformed, and other additional information) Stage of disease (Stage I, II, III, IV; constitutional symptoms A, B; Subtype E, X, S)
- Cytogenetic analysis (results available yes, t(11;14), t(11q), +12, del(11q), del(13q), del(17p), t(14;18), t(8;14), t(8;22), other)
- Immunophenotypic analysis (results available yes; IgVH status mutated, unmutated, not applicable; CD5, CD10, CD19, CD20, CD21, CD23, CD43, CD79b, BCL1, BCL2, BCL6, CYCLIN D1, ZAP70 negative, positive, not done)

Prior anticancer procedure or therapy will include the following variables:

- Number of lines of therapy/regimens per patient
- Response to the first line and/or most recent line of prior systematic therapy
- Any prior radiotherapy for the current malignancy (yes, no)
- Any prior surgery for the current malignancy (yes, no)
- Reason for stopping therapy (progression, toxicity, other)
- Best response (complete response [CR], partial response [PR], stable disease [SD], progressive disease [PD], not evaluable [NE])
- Any prior stem cell transplant (yes, no)
- Type of transplant (allogenic, autologous, both, other)
- Conditioning therapy (yes, no)

Medical and cancer history data will be listed. Results of cytogenetic analysis and immunophenotypic analysis will be listed. Tumor tissue biopsy collection will not be listed, but will be contained in datasets.

Prior anticancer surgery, radiotherapy, systemic therapy, and stem cell transplant data will be listed.

4.6 Prior or Concomitant Medications (other than anticancer therapies)

All medications taken from the ICF signature date or within 14 days prior to Cycle 1 Day 1 (C1D1), whichever is earlier, and until at least 30 days after last dose of study drug are to be reported in the CRF pages.

All medications will be coded using the World Health Organization-Drug Dictionary (WHO-DD).

- Prior medications are those the patient used prior to the first dose. Prior medications can be discontinued before the first dose or can be ongoing during the treatment phase.
- Concomitant medications are any treatments received by the patient concomitantly to any loncastuximab tesirine from the first dose to the last dose + 30 days. A given medication can be classified both as a prior medication and as a concomitant

medication. Concomitant medications do not include medications started 30 days after the last dose.

Any technical details related to computation, dates, and imputation for missing dates are described in Section 7.

Prior medications will be listed together with concomitant medications.

4.7 Exposure to Treatment

4.7.1 Extent of Loncastuximab Tesirine Exposure

Loncastuximab tesirine exposure will be summarized for the all-treated population. Duration of treatment, total number of cycles dosed, total dose received (in μg and $\mu\text{g}/\text{kg}$), average dose per cycle (in μg and $\mu\text{g}/\text{kg}$), and relative dose intensity (actual dose taken / planned dose) will be tabulated. Patients will receive 150 $\mu\text{g}/\text{kg}$ every 3 weeks (Q3W) for 2 cycles, then 75 $\mu\text{g}/\text{kg}$ Q3W for subsequent cycles as planned. When actual weight adjusted dose is needed, the last available weight before each infusion will be used. Patients with a BMI ≥ 35 kg/m^2 will have their dose calculated based on an adjusted body weight as follows:

$$\text{Adjusted body weight in kg} = 35 \text{ kg}/\text{m}^2 * (\text{height in meters})^2$$

Dose administered at each infusion (μg) is calculated by concentrated investigational product (IP) volume (in mL) * 5 mg/mL * 1000. For incomplete infusion, adjust the calculated prepared dose by multiplying a factor of (1- volume of dosing solution not administered [in mL]/ 50 mL) for concentrated solution formulation, or (1- volume of dosing solution not administered [in mL]/ [50 + total volume of reconstituted solution] mL) for lyophilized formulation. The number of patients who received loncastuximab tesirine at each cycle will also be tabulated using frequency counts and percentages.

Dose delays and dose reductions may also be analyzed if relevant. A cycle is delayed if it starts more than 2 days post- scheduled date.

Relative dose intensity will be additionally presented categorized (<60%, ≥ 60 - <80%, ≥ 80 - <90%, ≥ 90 - <110%, $\geq 110\%$).

Exposure data and infusion details will be listed together.

4.7.2 Prophylactic Medications for Hypersensitivity

Prophylactic medications for hypersensitivity will be listed only.

4.7.3 Subsequent Anticancer Therapy or Procedure

Patients' subsequent anticancer therapies or procedures including systemic therapy, radiation, transplant, or other, along with the start date of new anticancer therapy or procedure will be collected and listed only.

4.8 Safety Analyses

The summary of safety results will be presented.

General common rules

All safety analyses will be performed on the all-treated population, unless otherwise specified, using the following common rules:

- The baseline value is defined as the last non-missing value or measurement taken up to the first dose in the study.
- The analyses of the safety variables will be essentially descriptive and no systematic testing is planned.
- If relevant, selected safety analyses will be summarized by age, sex, racial subgroups, and any pertinent subgroups.
- The toxicity grade according to the Common Terminology Criteria for Adverse Events (CTCAE) version 4.0 will be taken into account in the summary. For patients with multiple occurrences of the same event, the maximum grade is used. If a patient has both missing and non-missing severity grades for treatment-emergent adverse events (TEAEs) within the same preferred term (PT), the patient will be counted under the non-missing severity grade.

4.8.1 Adverse Events, Serious Adverse Events, and Deaths

4.8.1.1 Analyses of adverse events

The primary focus of adverse event reporting will be on TEAEs. An adverse event (AE) will be considered to be a TEAE if it begins or worsens on or after the first dose date and until 30 days after the last dose date, or start of a new anticancer therapy/procedure, whichever comes earlier.

An AE occurring before the first dose or more than 30 days after the last dose date or after the start of a new anticancer therapy/procedure will not be included in TEAE displays, but will be listed as non-TEAEs.

If an AE date/time of onset (occurrence, worsening, or becoming serious) is incomplete, an imputation algorithm will be used to classify the AE as pre-treatment, TEAE, or post-treatment. The algorithm for imputing date/time of onset will be conservative and will classify an AE as treatment-emergent unless there is definitive information to determine it is a non-TEAE (pre- or post-treatment). Some details on classification of AEs with missing or partial onset dates are provided in Section 7.

Analysis of all TEAE(s):

The following TEAE summaries will be generated for the all-treatment population.

- Overview of TEAEs, summarizing number of TEAE and number (%) of patients with any
 - TEAE
 - Related TEAE (including possibly related, probably related, or related)

- Any TEAE \geq Grade 3
- Serious TEAE
- TEAE leading to death
- TEAE leading to permanent treatment withdrawal
- TEAE leading to loncastuximab tesirine delay or reduction or interruption (if applicable)
- TEAE with at least one infusion related reaction
- All TEAEs \geq Grade 3 by PT, showing number (%) of patients with at least one TEAE, sorted by decreasing incidence of PTs
- All TEAEs by primary System Organ Class (SOC) and PT, showing number (%) of patients with at least one TEAE, sorted by SOC in alphabetic agreed order and decreasing incidence of PTs within SOC. This sorting order will be applied to all other tables, unless otherwise specified.
- All TEAEs by primary SOC, PT and Maximal CTCAE grade, showing number (%) of patients with at least one TEAE, sorted by SOC and PT in alphabetic order. This sorting order will be applied to all other tables, unless otherwise specified.
- All TEAEs \geq Grade 3 by primary SOC, PT and Maximal CTCAE grade
- All related TEAEs by primary SOC, PT and Maximal CTCAE grade (including possibly related, probably related, or related)
- All TEAEs leading to treatment withdrawal by primary SOC, PT and Maximal CTCAE grade
- All TEAEs leading to dose delay by primary SOC, PT and Maximal CTCAE grade
- All TEAEs leading to dose reduction by primary SOC, PT and Maximal CTCAE grade
- All TEAEs leading to infusion interruption by primary SOC, PT and Maximal CTCAE grade
- All TEAEs with fatal outcome by primary SOC, PT and Maximal CTCAE grade
- All Serious TEAEs by primary SOC, PT and Maximal CTCAE grade
- All infusion related reaction TEAEs by primary SOC, PT and Maximal CTCAE grade
- Summary of grouped TEAEs selected by Standardised MedDRA Query (SMQ), ADCT modified SMQ will also be provided by primary Grouped terms, PT and Maximal CTCAE grade. These group term include: effusion/edema, hepatic, fatigue, skin/nail, pain.

- Summary of TEAEs will also be provided by demographic factors including: sex, age group, race, disease subtype if appropriate.

All TEAEs, all serious adverse events (SAEs), all TEAEs leading to treatment withdrawal, all TEAEs leading to dose reduction, all TEAEs leading to dose delay, all TEAEs considered infusion related reactions, all TEAEs with fatal outcome and non-TEAEs will be listed.

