1.3 Safety and Efficacy of Loncastuximab Tesirine in Phase 1 Study, ADCT-402-101

ADCT-402-101 (NCT02669017) is a first-in-human Phase 1 dose-escalation study of loncastuximab tesirine in relapsed or refractory B-cell NHL patients, who have failed or are intolerant to established therapies, or have no other treatment options available. The study design involves a dose escalation phase (Part 1) followed by a dose expansion phase (Part 2). The primary objectives for Part 1 were to evaluate the safety and tolerability of loncastuximab tesirine and to determine the maximum tolerated dose (MTD) and/or the recommended dose(s) to use in Part 2. The primary objective for Part 2 was to evaluate the safety and tolerability of the dose(s) determined in Part 1. The secondary objectives include evaluating the clinical activity of loncastuximab tesirine as measured by ORR, DOR, progression free survival (PFS), and overall survival (OS).

As of data cut-off date of 03 December 2017, a total of 144 patients with relapsed or refractory B-cell NHL received at least one infusion of loncastuximab tesirine. The median age was 63.5 years (range: 23-86). The median number of previous chemotherapy regimens was 3 (range: 1-10) with 24.3% of patients having prior stem cell transplant.

Treatment-emergent adverse events (TEAEs) were reported in 137 (95.1%) out of 144 patients treated with loncastuximab tesirine. The most common TEAEs (observed in at least in 15% of patients), regardless of relationship to study treatment, were fatigue (42.4%); nausea (27.1%); gamma-glutamyltransferase (GGT) increased (26.4%); anemia (25.7%); edema peripheral (25.0%); dyspnea (18.8%); neutrophil count decreased, platelet count decreased, and thrombocytopenia (18.1% each); rash (17.4%); abdominal pain (16.0%); neutropenia (16.0%); and constipation (15.3%). Grade ≥ 3 TEAEs were reported in 92 (63.9%) patients. The most common Grade ≥ 3 TEAEs (observed in at least in 5% of patients) were neutrophil count decreased (16.0%); GGT increased (14.6%); anemia (12.5%); platelet count decreased (11.8%); neutropenia (11.1); and thrombocytopenia (8.3%).

The following events were considered non-serious adverse drug reactions (ADRs): GGT increased, edema (includes peripheral and facial), neutrophil count decreased, platelet count decreased, thrombocytopenia, neutropenia, and skin-related events (such as rash, maculopapular rash, and erythema).

TEAEs in 16 (11.1%) patients led to treatment discontinuation.

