2.2 Rationale for Dose Selection

For patients with relapsed or refractory non-Hodgkin lymphoma, available data support a loncastuximab tesirine dosing regimen of 150 $\mu\text{g}/\text{kg}$ every 3 weeks (Q3W) \times 2 cycles, followed by a 50% reduction to 75 $\mu\text{g}/\text{kg}$ Q3W for the Phase 2 trial. For safety, particular differences in predicted probabilities (pp) were apparent between the 200 $\mu\text{g}/\text{kg}$ Q3W and 150 $\mu\text{g}/\text{kg}$ Q3W doses, respectively, including Grade ≥ 3 edema (pp=0.2817 vs. 0.1070 in patients with prior stem cell transplant), liver function test-related toxicities (pp=0.4018 vs. 0.1644 in patients with prior relapsed disease; 0.4018 vs. 0.1644 in patients without prior stem cell transplant; pp=0.5208 vs. 0.2203 in patients with body mass index [BMI] of 35 kg/m^2 , and pp=0.4018 vs. 0.1644 in patients with baseline Eastern Cooperative Oncology Group [ECOG] of 0 or 1, respectively), and neutropenia or neutrophil decrease (pp=0.4383 vs. 0.2865).

For efficacy, the decision for initial dosing at the 150 µg/kg dose level is predicated on higher observed and predicted ORR as compared to the 120 µg/kg and lower doses. The decision to dose reduce following 2 cycles of treatment was based on the rapid onset of response observed in a majority of patients (median 2 cycles), and desire to mitigate onset of late-developing and difficult to manage toxicities, such as edema. Initial dosing for 2 cycles is anticipated to optimize the frequency of objective response, while dose reduction in subsequent cycles will permit continued exposure with manageable toxicity to optimize the durability of response.

3 Study Objectives and Endpoints

Table 2. Study Objectives and Endpoints

Objectives	Endpoints
Primary	
Evaluate the efficacy of single agent loncastuximab tesirine in patients with relapsed or refractory DLBCL	ORR according to the 2014 Lugano classification (Cheson et al. 2014) as determined by central review in all treated patients; ORR is defined as the proportion of patients with a best overall response (BOR) of CR or PR
Secondary	

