6.4 Dose Delays and Modifications

If a patient experiences any Grade ≥ 3 (≥ 2 for edema, effusion, or increased AST/ALT/GGT) non-hematologic toxicity, loncastuximab tesirine must be held until the toxicity resolves to Grade ≤ 1 (Grade 1 or baseline for peripheral neuropathy). In addition, if a patient experiences hematological toxicity of Grade ≥ 3 neutropenia or thrombocytopenia, loncastuximab tesirine must be held until the toxicity resolves to Grade ≤ 2 .

If loncastuximab tesirine dosing is delayed by more than 3 weeks and the toxicity is considered at least possibly related to loncastuximab tesirine, then subsequent doses of loncastuximab tesirine will be reduced by 50%. In addition, the Investigator may reduce the dose of loncastuximab tesirine by 50% for any Grade ≥ 3 (≥ 2 for edema, effusion, or increased

AST/ALT/GGT) toxicity that is possibly related to loncastuximab tesirine, but does not result in dosing delay of more than 3 weeks if they feel it is in the best interest of the patients.

If toxicity requiring dose reduction as described above occurs following the second dose of 150 µg/kg (C2D1), the patient should receive the per protocol-defined dose of 75 µg/kg for Cycle 3.

If toxicity as described above recurs at the reduced dose, subsequent doses of loncastuximab tesirine will be reduced by an additional 50%.

If toxicity as described above recurs after a second dose reduction, study drug must be discontinued permanently.

If loncastuximab tesirine dosing is delayed by more than 5 weeks and the toxicity is considered at least possibly related to loncastuximab tesirine, study drug must be discontinued permanently unless continued administration is approved by the Sponsor.

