- 14.3.3.4.13 Treatment-emergent Adverse Events by System Organ Class, Preferred Term, and Maximum CTCAE Grade for Female Patients (All-Treated Population)
- 14.3.3.4.14 Treatment-emergent Adverse Events by System Organ Class, Preferred Term, and Maximum CTCAE Grade for Male Patients (All-Treated Population)
- 14.3.3.4.15 Treatment-emergent Adverse Events by System Organ Class, Preferred Term, and Maximum CTCAE Grade for Patients Age <65 years old (All-Treated Population)
- 14.3.3.4.16 Treatment-emergent Adverse Events by System Organ Class, Preferred Term, and Maximum CTCAE Grade for Patients Age between 65 - 74 years old (All-Treated Population)
- 14.3.3.4.17 Treatment-emergent Adverse Events by System Organ Class, Preferred Term, and Maximum CTCAE Grade for Patients Age ≥75 years old (All-Treated Population)
- 14.3.3.4.18 Treatment-emergent Adverse Events by System Organ Class, Preferred Term, and Maximum CTCAE Grade for Patients in USA (All-Treated Population)
- 14.3.3.4.19 Treatment-emergent Adverse Events by System Organ Class, Preferred Term, and Maximum CTCAE Grade for Patients in United Kingdom (All-Treated Population)
- 14.3.3.4.20 Treatment-emergent Adverse Events by System Organ Class, Preferred Term, and Maximum CTCAE Grade for Patients in Italy (All-Treated Population)
- 14.3.3.4.21 Treatment-emergent Adverse Events by System Organ Class, Preferred Term, and Maximum CTCAE Grade for Race = White (All-Treated Population)
- 14.3.3.4.22 Treatment-emergent Adverse Events by System Organ Class, Preferred Term, and Maximum CTCAE Grade for for Race other than White (All-Treated Population)
- 14.3.3.4.23 Treatment-emergent Adverse Events with Grade ≥3 by System Organ Class, Preferred Term, and Maximum Severity (All-Treated Population)
- 14.3.3.4.24 Selected Treatment-emergent Adverse Events by Grouped AE, Preferred Term, and Maximum Severity (All-Treated Population)

14.3.3.4.25 Summary of Adverse Events \geq Grade 3 suggestive of Selected Conditions for Patients Undergo Stem Cell Transplant after Discontinuation of Study Drug (Stem Cell Transplant Population)

Note: conditions includes hepatic toxicity, veno-occlusive disease/sinusoidal obstruction syndrome, graft-versus-host disease, infectious complications, prolonged cytopenia(s), and pulmonary toxicity

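### The SAP names no grouped adverse-event term for neutropenia or thrombocytopenia, so no named AE summary counts each patient once for either combined event

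*SAP*

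**What the plan says.** SAP 4.8.1.1 builds its AE summaries on preferred terms (PTs), alone or within system organ class (SOC). Protocol 9.7.1 counts a patient once per PT, or once per SOC, at the worst grade. PTs are combined only in one grouped summary: "These group term include: effusion/edema, hepatic, fatigue, skin/nail, pain". The matching output in SAP Appendix 2 is Table 14.3.3.4.24, "Selected Treatment-emergent Adverse Events by Grouped AE, Preferred Term, and Maximum Severity"; its entry adds no further group.

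Four other places bear on this:

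- Protocol 1.3 describes the Phase 1 study, in which "a total of 144 patients with relapsed or refractory B-cell NHL received at least one infusion of loncastuximab tesirine". Its list of common events of Grade 3 or higher gives "neutrophil count decreased (16.0%); GGT increased (14.6%); anemia (12.5%); platelet count decreased (11.8%); neutropenia (11.1); and thrombocytopenia (8.3" (all percentages).
- The any-grade list in the same section gives "neutrophil count decreased, platelet count decreased, and thrombocytopenia (18.1% each", with neutropenia separately at 16.0%.
- Protocol 2.2, on dose selection, treats the two neutrophil terms as one event: "neutropenia or neutrophil decrease (pp=0.4383 vs. 0.2865", for 200 and 150 µg/kg respectively.
- Protocol 6.4 sets a mandatory hold for hematological toxicity and names only two kinds, at Grade 3 or higher: "neutropenia or thrombocytopenia, loncastuximab tesirine must be held until the toxicity resolves".

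**The concern.** In this drug's own data each cytopenia was reported under two PTs. A table with one row per PT then shows two partial counts, and a patient who has both terms appears in both rows. The two rows cannot simply be added, and the larger one may fall short of the number of patients affected. SOC rows do not help, because they count any event in the class.

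The SAP already combines terms for hepatic and edema events, which also have their own threshold in Protocol 6.4. It does not do so for the two cytopenias that trigger a hold in the same section. The practical loss is in the tables that attach a consequence to the event. From the related, dose-delay, dose-reduction and withdrawal tables, a reader could not say how many patients had dosing delayed for low neutrophils; only a range could be given. Characterizing the safety profile is a secondary objective (SAP 2.2).

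**Working it through.** **Inputs.** All rates are from Protocol 1.3, with N = 144 treated patients.

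**Step 1: recover the counts.** For each percentage, find the integer x for which 100·x/144 rounds to it. Each has exactly one solution, so the Phase 1 figures reproduce.

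| Term | Grade ≥3 | Count | Any grade | Count |
|---|---|---|---|---|
| Neutrophil count decreased | 16.0% | 23 | 18.1% | 26 |
| Neutropenia | 11.1% | 16 | 16.0% | 23 |
| Platelet count decreased | 11.8% | 17 | 18.1% | 26 |
| Thrombocytopenia | 8.3% | 12 | 18.1% | 26 |

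For comparison at Grade ≥3: GGT increased is 14.6% (21) and anemia 12.5% (18).

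**Step 2: bound the combined event.** If a and b patients have the two terms, the number with either lies between max(a, b), when overlap is complete, and a + b, when there is none. If the terms occurred independently it would be a + b − ab/144.

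- Grade ≥3 neutrophils: max(23, 16) = 23 to 23 + 16 = 39, so 23/144 = 16.0% to 39/144 = 27.1%. Independence: 39 − 23·16/144 = 36.4, or 25.3%.
- Grade ≥3 platelets: 17 to 17 + 12 = 29, so 11.8% to 20.1%. Independence: 29 − 17·12/144 = 27.6, or 19.2%.
- Any-grade neutrophils: 26 to 26 + 23 = 49, so 18.1% to 34.0%.
- Any-grade platelets: 26 to 26 + 26 = 52, so 18.1% to 36.1%.

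**Step 3: compare with the largest single row.** At Grade ≥3 the possible shortfall is 0 to 16 of 144 patients for neutrophils (0 to 11.1 points; at most 39/23 = 1.7-fold). For platelets it is 0 to 12 of 144 (0 to 8.3 points; at most 29/17 = 1.7-fold).

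**Step 4: scale to 140 patients.** This assumes that Phase 1 rates apply here.

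- Neutrophils: the largest row would show 140·23/144 = 22.4 patients, against up to 140·39/144 = 37.9 for the combined event.
- Platelets: 140·17/144 = 16.5 against up to 140·29/144 = 28.2.

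**Step 5: check the ranking.** The neutrophil term leads the Phase 1 Grade ≥3 list whether split or combined. The platelet pair does not clearly do so. Its larger term (17) is below GGT (21) and anemia (18), and the pair exceeds GGT only at 22 or more patients. That requires an overlap of at most 29 − 22 = 7 of the 12 thrombocytopenia patients.

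**The case against.** The strongest reply is that low neutrophils and platelets are laboratory quantities and that the SAP reports them unsplit. SAP 4.8.2 and Appendix 2 plan three relevant hematology tables:

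- shifts by maximum CTCAE grade (14.3.4.4.1);
- shifts from Grade 2 or lower at baseline to Grade 3 or higher (14.3.4.4.1a);
- maximum post-baseline grade (14.3.4.7.1).

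Each counts a patient once per parameter, whichever PT was reported, and unscheduled values enter the worst-case summaries. This stands. A reader might infer that the cytopenias are hidden from the report, and the documents do not support that. What the laboratory tables lack is relatedness, seriousness and action on dosing. They also measure something different, because Protocol 8.3.5 makes only clinically significant abnormal results adverse events.

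A second reply is that the list is open. The SAP says that the groups include the five, and Appendix 2 allows the list of outputs to change without a SAP update. This also stands, so the accurate statement is that no cytopenia group is named, not that none can be produced. But nothing commits the sponsor to adding one, and in an open-label single-arm trial groups are better fixed before the results are known. The planned patient listings would allow a recount, but that is no substitute for a planned summary.

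Three further inferences are tempting and go too far:

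- That the rates *are* understated. The overlap is not given, so the shortfall may be zero, and each PT row is correct as a count of that PT.
- That both cytopenias are the most frequent severe toxicities. Step 5 supports this for neutrophils only.
- That 0.2865 in Protocol 2.2 is a benchmark for this trial. It is a model prediction for 150 µg/kg every 3 weeks, whereas this trial gives that dose for two cycles and 75 µg/kg afterwards. Section 2.2 does not make clear whether the grade given for edema also applies to the neutrophil event. The figure shows only that the sponsor regards the two terms as one event.

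**Conclusion.** The point holds as a gap in the named AE summaries and is a cheap improvement. It does not touch the primary endpoint, any test or the interim rule. SAP 4.8.1.1 leaves two events that trigger a mandatory hold without a named group, although Phase 1 reported both terms of each pair.

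At Phase 1 rates the largest Grade 3 or higher row may fall short of the combined event by 0 to 11.1 points for neutropenia and 0 to 8.3 points for thrombocytopenia. Two assumptions lie behind this size. First, both PTs of each pair will again be used in this trial, with an unknown overlap. Second, rates from all doses and all B-cell NHL carry over to DLBCL patients on this regimen. The gap itself, with no planned once-per-patient count by relatedness or dosing action, does not depend on the size.

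**What to change.** In SAP 4.8.1.1 and Table 14.3.3.4.24, add two groups with their terms listed: neutropenia (PTs neutropenia and neutrophil count decreased) and thrombocytopenia (PTs thrombocytopenia and platelet count decreased). Count each patient once at maximum grade.

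State whether febrile neutropenia is inside or outside the neutropenia group. Protocol 1.3 reports it as a dose-limiting toxicity in one patient and as a possibly related serious event in five, so the choice affects the count.

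Show the same grouped rows in the related, Grade 3 or higher, dose-delay, dose-reduction and withdrawal tables, and keep the individual PT rows beneath them.

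The cost is a short addition to the SAP and a few programmed rows, with no new data. The downside for the sponsor is that the stated cytopenia rates may look less favourable than the single-PT rows.
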